7.1.4. Procedures for reporting of adverse events

Assessing of adverse events

Data on AEs will be obtained at scheduled or unscheduled trial visits, based on information spontaneously provided by the subject and/or through questioning of the subject. AE data may also be obtained from subject’s diary cards, but information thus collected must be reviewed and assessed medically before it is transcribed to the eCRF.

If a subject is seen by a physician not involved in the trial because of an adverse event, the investigator should make every effort to contact the treating physician in a timely manner in order to obtain all information necessary to appropriate reporting of the event.

Recording of adverse events

Complete description of all adverse events must be available in the source documents.

All AEs including local and systemic reactions should be captured on the appropriate pages of the eCRF.

Information to be recorded, based on above assessment criteria, includes event description, its duration (time of onset and time of resolution), its severity, whether it is considered serious (and if so the criterion satisfied), its relationship to IMP, any action taken (concerning the IMP or other) and its outcome.

Any AE that is still ongoing after final visit will be left as ongoing in the eCRF. However, the investigator will continue to follow up ongoing SAEs and record information in the source documents and on the Follow-Up SAE Form, until resolution or no further improvement can be expected.

AEs must be recorded on the eCRF according to the following guidelines:

- Whenever possible, recognised medical terms should be used to describe an AE rather than colloquialism (e.g. “influenza” rather than “flu”) and abbreviations should be avoided.
- The description of an AE should use a specific clinical diagnosis, if this is available, rather than a list of component signs or symptoms (e.g. “congestive heart failure” rather than “dyspnea, rales and cyanosis”).
- Signs and symptoms that are not linked to an identified disease or syndrome, or for which an overall diagnosis is not available, should be reported separately, as individual AEs.
- Provisional diagnosis (e.g. “suspected myocardial infarction”) is acceptable but should be followed up to a definite diagnosis if finally available.

Reporting of adverse events

Complete and accurate data on all AEs experienced, for the duration of the reporting period, will be reported on an ongoing basis in the AE pages of the eCRF.

The period of observation for the collection of AEs extends from the time when the subject gives informed consent until the date of final visit.

Serious adverse events occurring after a subject has taken the last dose of IMP will be collected until the date of final visit, regardless of the investigator's opinion of causation. Thereafter, SAEs are not required to be reported unless the investigator feels the events were related to either IMP administration or to a protocol procedure.

All AEs with onset or worsening after first intake of IMP until 7 days after last intake of IMP are defined as treatment emergent.

If a subject is documented as lost-to follow-up, ongoing/unknown outcome AEs will not be followed up.

For screening failure subjects, new AEs and updates must be recorded in the source and trial documents until the date the subject is determined to be a screening failure. Beyond this date, only SAEs will be followed up by CRO's pharmacovigilance representative.

7.2. Serious Adverse Event (SAE)

7.2.1. Definition of a serious adverse event

A serious adverse event (SAE) is defined as an AE which at any dose meets one of the following conditions:

- Death during the period of protocol defined surveillance, i.e. the AE causes or contributes to the death. In case of fatality, the cause of death is considered as the AE, and the death is its outcome.
- Life threatening event (defined as a subject at immediate risk of death at the time of the event), i.e. the AE places the subject at immediate risk of death (the definition does not apply to an AE that hypothetically might cause death if it was more severe).
- An event requiring inpatient hospitalisation or prolongation of existing hospitalisation during the period of protocol defined surveillance, i.e. the AE requires at inpatient hospitalisation or prolongs a hospitalisation beyond the expected length of stay.
- Hospital admissions are not to be considered as SAE according to this criterion in the following purposes: surgery planned before trial entry, social reasons, normal disease management (including treatment adjustment), if the protocol procedures or the standard management of the disease under study requires planned hospitalisations.
- Results in a persistent or significant disability/incapacity, i.e. the AE resulted in a substantial disruption of the subject's ability to conduct normal activities.
- Any other important medical condition, i.e. AE that may not immediately result in death, be life threatening, or require hospitalisation, but is clearly of major clinical significance. Based upon appropriate medical judgment, the event may jeopardise the subject or may require medical or surgical intervention to prevent one of the serious outcomes listed above. Examples of such medical events include allergic bronchospasm requiring intensive treatment in an emergency room or at home, blood dyscrasia or convulsions that do not result in inpatient hospitalisation, or the development of drug dependency or drug abuse.

Any serious adverse event requires an expedited reporting to the pharmacovigilance delegate regardless of its relationship to the IMP.

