 8. Other active clinically significant illness, including unstable cardiovascular or malignant pathology, significant abnormality in physical examination or clinical laboratory results at VS1, which could interfere with the trial conduct or counter-indicate the trial treatments or place the subject at risk during the trial or compromise the trial participation.
 9. Subjects with hepatic impairment (serum total bilirubin \geq 2 mg/dL, except in patients diagnosed with Gilbert's syndrome, or prothrombin time [PT] \geq 13.7 s (except in patients on therapeutic anti-coagulation), or serum albumin < 3.5 g/dL), or renal impairment (glomerular filtration rate [GFR] < 60 mL/min/1.73 m², according to Kidney Disease Improving Global Outcomes (KDIGO, [32])).
 10. Known hypersensitivity to IMP (active ingredients or excipients of modafinil or flecainide capsules).
 11. Subjects currently (or within 6 weeks before VS1) under one of the following medications (isolated intake up to 1 week can be accepted):
 - a. Neuroleptics, anxiolytics, anticonvulsants. Benzodiazepines and benzodiazepine-like drugs are only authorised if used regularly at stable indicated doses with an evening intake as sleep promoting agents.
 - b. Flecainide or other class I antiarrhythmic drugs (see Section 14.3).
 - c. Psychostimulants (except caffeine if no abuse and stable consumption) such as, but not limited to, modafinil, methylphenidate, amphetamine.
 - d. Antidepressants except if maintained at stable dose for at least 6 weeks prior to VS1 and anticipated to remain stable during the trial in subjects with mild or moderate unipolar depression.
 - e. Antiemetic medications (except domperidone), myo-relaxing drugs and opioids.
 - f. Dopaminergic medications, unless they have been used at stable doses for at least 4 weeks before screening and it is anticipated that the doses will not be changed throughout the trial. Efficacious medication for Parkinson's disease should not be discontinued for the sole purpose of the subject's enrolment into this clinical trial but must be maintained at stable dosage levels.
 - g. Centrally acting anti-obesity drugs.
 - h. TNF-alpha inhibitors.
 12. Pregnancy or lactation. Women of childbearing potential who intend to be pregnant during the next few months.
 13. Subjects protected by the law (legal guardianship).

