7. ADVERSE EVENT, PREGNANCY AND EMERGENCY

7.1. Adverse Event (AE)

7.1.1. Definition of an adverse event

An adverse event is any untoward medical occurrence in a clinical trial subject administered a medicinal product and which does not necessarily have a causal relationship with this treatment.

AEs can be symptoms, signs, or clinically relevant laboratory abnormalities occurring during the course of the trial.

All other medical conditions, which are present at VS1, should not be considered as AEs unless a worsening in severity or frequency has occurred during the trial. These medical conditions should be adequately documented on the appropriate page of the eCRF.

When reporting abnormal laboratory results on the AE pages of the eCRF, a clinical diagnosis should be recorded rather than the abnormal value itself if this is available (e.g. “anaemia” rather than “decreased red blood cell count” or “haemoglobin = 10.5 g/dL”).

In case of surgical or diagnostic procedures, the condition/illness leading to such a procedure is considered as the AE rather than the procedure itself.

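### The disease-management exemption in the SAE definition has no reference date and does not exclude worsening, so an in-trial admission for deteriorating Parkinson's disease could be classed as non-serious

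*Protocol*

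**What the plan says.** Protocol 7.2.1 includes among the seriousness criteria "An event requiring inpatient hospitalisation or prolongation of existing hospitalisation during the period of protocol defined surveillance". The next item narrows it: "Hospital admissions are not to be considered as SAE according to this criterion in the following purposes: surgery planned before trial entry". The list then continues with "social reasons, normal disease management (including treatment adjustment), if the protocol procedures or the standard management of the disease under study requires planned hospitalisations".

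Protocol 7.1.1 deals with conditions already present at VS1. They "should not be considered as AEs unless a worsening in severity or frequency has occurred during the trial". Protocol 7.1.4 requires "Complete and accurate data on all AEs experienced, for the duration of the reporting period, will be reported on an ongoing basis", and it counts worsening after the first intake of study drug, up to 7 days after the last, as treatment emergent.

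On background therapy, exclusion criterion 11f in Protocol 4.3 says that effective Parkinson's medication should not be withdrawn just to enrol a subject, "but must be maintained at stable dosage levels". Protocol 5.5 repeats this for the trial period. Protocol 6.2.3 allows a change of concomitant dose where efficacy or safety makes it necessary.

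SAP 5.5.1 takes serious status from the investigator's assessment alone. It also lists, among the other actions recorded for an adverse event, whether hospital admission was needed or extended.

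**The concern.** The exemption names treatment adjustment as a reason for an admission not to count. In a trial where Parkinson's medication is meant to stay stable, an in-trial admission to adjust it may be a safety signal. Protocol 7.1.1 would make the underlying worsening an adverse event, and 7.2.1 could then take away the hospitalisation ground for calling it serious. Nothing reconciles the two sections.

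The serious flag has consequences. Without it there is no 24-hour report (Protocol 7.2.3) and no assessment for expedited reporting, which is confined to serious and unexpected events (Protocol 7.2.4). Follow-up beyond the final visit is also not required, because other ongoing adverse events are left as ongoing (Protocol 7.1.4). In the SAP the event moves from the serious to the non-serious table. Safety is the primary objective (Protocol 2.1), and with an estimated 28 sites an ambiguous rule can be applied in different ways.

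**Working it through.** The plan states no figure for this point. The check is a reading of the sections against each other, followed by an illustration of scale.

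**1. Scope of the exemption.** It removes admissions from seriousness only under the hospitalisation criterion. Death, immediate threat to life, persistent or significant disability, and other important medical conditions remain available.

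**2. What the date limit governs.** In "Hospital admissions are not to be considered as SAE according to this criterion in the following purposes: surgery planned before trial entry" the words about planning before trial entry describe surgery. The later items carry no date.

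**3. What the closing condition governs.** In "normal disease management (including treatment adjustment), if the protocol procedures or the standard management of the disease under study requires planned hospitalisations" the last clause can be read in two ways.

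- *As a separate list item.* Any admission described as normal disease management, including treatment adjustment, is exempt from the hospitalisation criterion, planned or not.
- *As a condition on disease management.* Only planned admissions are exempt, so an unplanned admission for deterioration stays serious. This is the more natural reading. But planned has no reference date, so an admission arranged after study drug was started, because the patient had worsened, can still qualify.

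Both readings leave a gap; the second leaves a smaller one.

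**4. Whether the protocol-procedure part has a use.** Protocol 6.1 schedules seven on-site and five telephone visits. I find no procedure in section 6 that requires an inpatient stay.

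**5. What is still captured.** The worsening is an adverse event (7.1.1), must be entered in the eCRF (7.1.4), and is treatment emergent if it occurs on study drug. The admission itself is a recorded field (SAP 5.5.1).

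**6. Whether a later check would find the misclassification.** Neither document describes comparing the hospitalisation field with the serious flag. The adverse-event item in the blind data review (SAP 5.1.2, PD#30) concerns events that may affect the key efficacy or PK endpoints.

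**7. Scale, as illustration only.** Inputs: 60 randomised subjects and three treatment periods of 2 weeks (Protocol 3.1 and 4.1). It is assumed that all 60 receive each treatment.

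- Total exposure, placebo included: 60 × 6/52 = 6.9 patient-years.
- Exposure per treatment: 60 × 2/52 = 2.3 patient-years.
- One serious event on a dose: 1/60 = 1.7%, exact two-sided 95% upper limit 8.9%.
- The same event classed as non-serious: 0/60 = 0%, upper limit 1 − 0.025^(1/60) = 6.0%.

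This shows how far one classification moves a sparse table. It does not predict how often such an admission would occur.

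**The case against.** The strongest reply is that the gap is narrow and well backed up. The exemption is confined to one criterion. Two of the remaining criteria fit Parkinson's worsening well: substantial disruption of normal activities, and an important medical event that may need intervention to prevent a serious outcome. The text speaks of normal management and, read naturally, of planned admissions under standard care, so an investigator has to stretch it to cover deterioration on study drug. Dose changes are foreseen in Protocol 6.2.3, so an adjustment does not always mean harm. The severe grade in Protocol 7.1.2 mentions possible hospitalisation, so the event would probably also show in the table by severity. MDS-UPDRS is summarised by treatment. Protocol 7.2.4 also requires expedited reporting of other new information that might influence the benefit-risk assessment.

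Most of this stands, and it rules out three stronger inferences that a reader might draw.

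- *Such events go unreported.* They do not: they must be recorded as adverse events, with the admission as a data field. What can be missing is the report as a serious event.
- *The event loses all seriousness.* It does not: the other criteria are untouched.
- *The primary safety objective is biased.* The documents do not show this. The rule applies blinded and alike under all three treatments, overall adverse event incidence is unchanged, and nothing indicates how often such admissions occur. The possible loss is sensitivity in the serious-event tables and in expedited reporting.

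The reply does not close the gap. The important-medical-event criterion rests on judgement, whereas admission is an observable fact. The natural reading still leaves planned undated, and no section says that an admission caused by worsening falls outside the exemption.

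**Conclusion.** The point holds in a limited form. The disease-management exemption is not tied to planning before trial entry, does not exclude worsening, and ends in a clause of unclear reach. An admission arranged during the trial because Parkinson's disease worsened could therefore appear only as a non-serious treatment-emergent event, without the 24-hour report, expedited assessment or a place in the serious-event tables. This assumes that no other seriousness criterion is judged to be met and that the investigator regards the admission as normal management.

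The size cannot be estimated from the documents. The upper limits of 8.9% and 6.0% illustrate the effect of one event and concern the serious-event rate only. The correction is worth making because it is cheap and bears on safety reporting, which serves the primary objective.

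**What to change.** Reword the exemption in Protocol 7.2.1, and the SAE form instructions to match:

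- The disease-management exemption applies only to admissions planned before VS1 or required by protocol procedures.
- It never applies to an admission caused by an adverse event, including worsening of Parkinson's disease as described in 7.1.1.
- An admission with no untoward event is not an SAE. Treating every admission after VS1 for treatment adjustment as serious would go too far, because 7.2.1 requires an SAE to be an adverse event first.

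Add a step to the data review before database lock: list adverse events for which hospital admission was needed or extended but which are not flagged serious, and query the investigator. The investigator keeps the seriousness assessment, so the SAP definition of an SAE need not change. This step is useful even if the protocol wording can no longer be amended.

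The cost is a short wording change, one extra listing with its queries, and possibly a few more SAE reports.

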7.2.2. Definitions of Suspected Unexpected Serious Adverse Reactions (SUSAR)

Suspected unexpected serious adverse reaction (SUSAR) is an adverse reaction, the nature or severity of which is not consistent with the applicable product information (e.g. investigator's brochure for an unauthorised investigational product or summary of product characteristics for an authorised product).

7.2.3. Procedures for reporting of SAEs and SUSARs

All serious adverse events must be recorded on the SAE report form, followed through resolution by the investigator.

The investigator must complete the SAE report form and notify the CRO's pharmacovigilance delegate, be it a new SAE or new information on a previously reported SAE (i.e. so-called SAE follow-up), within the following timelines:

- The investigator must report all SAEs to the CRO's pharmacovigilance delegate within 24 hours of identifying the SAE.
- Other supporting documentation of the event may be requested by CRO's pharmacovigilance delegate and should be provided as soon as possible.
- All reportable SAEs will be followed until satisfactory resolution or until the investigator deems the event to be chronic or the subject to be stable.

The SAE report form must be sent directly to the CRO's pharmacovigilance delegate by electronic mail or facsimile as specified below:

For any new SAE, the following minimum information is required as initial notification:

- Identification of the investigator,
- Subject identification details (subject number)
- IMP details (name, dose(s), route and date(s) of administration, indication)
- Diagnosis of the event (or an outcome) with the description (or a brief description of signs/symptoms/clinical course if the diagnosis is not available) and the date of onset
- Reason(s) for considering the event as serious
- Relationship of the event with the IMP or with the trial procedure (i.e. the causality according to the investigator).

Information about SAEs and important medical conditions with any relevant ongoing/unknown outcomes will be followed-up until resolution, even if eCRFs and database will no longer be updated. SAEs occurring after a subject has taken the last dose of trial drug will be collected until final study visit, regardless of the investigator's opinion of causation. Thereafter, serious adverse events are not required to be reported unless the investigator feels the events were related to either IMP administration or a protocol procedure.

7.2.4. Procedures for regulatory reporting of serious adverse events

Following notification by the investigator, sponsor or designee will report events that are both serious and unexpected (i.e. using the current version of the THN102 IB at the time of SAE reporting as reference) and that are associated with IMP to the competent authorities (CAs) in expedited reporting. Unblinding will be performed as described in Section 5.2.2 by opening the individual sealed envelope for the involved subject.

Moreover, any other new information that might influence the benefit-risk assessment of the IMP or that would be sufficient to consider changes in IMP administration or in the overall conduct of the clinical trial necessitate an expedited reporting to the CAs as well.

CAs should be notified of any expedited reporting within the required timelines as specified in ICH-E2A: fatal and life-threatening events within 7 calendar days (by phone/fax/writing/electronic communication) after first knowledge by CRO's pharmacovigilance delegate who will issue a complete report within 8 additional calendar days, with copy to investigator, CRA, CRO's trial manager, and sponsor. All other serious adverse events and SUSARs must be filed in writing within 15 calendar days after first knowledge by CRO's pharmacovigilance delegate.

All serious adverse events will be reported to the CAs in the development safety update report (DSUR) annually, if appropriate.

In accordance with the ICH GCP guidelines, the responsible person for pharmacovigilance on behalf of the sponsor Theranexus will inform the investigators of findings that could affect adversely the safety of the subjects, impact the conduct of the trial, or alter the IEC/IRB's approval/favourable opinion to continue the trial.

In particular, sponsor or designee will inform the investigators of SUSARs and serious adverse events that are considered to be related to the administered IMP. The investigators will keep copies of these safety reports in the investigator site file (ISF). National regulations with regards to safety reports notifications to investigators will be taken into account.

Unless clearly defined otherwise by national or site-specific regulations and duly documented, the clinical CRO will promptly notify the concerned IEC/IRB of any safety reports provided by the pharmacovigilance delegate and provide copies of all related correspondence to the CRA and the CRO's trial manager.

7.3. Pregnancy

Women of childbearing potential (defined as not surgically sterile or less than 2 years postmenopausal), must use a highly effective method of contraception, and must continue for the duration of the trial (and for 2 months after participation in the trial). Highly effective methods of contraception include: hormonal contraception associated with inhibition of ovulation (combined estrogen/progestogen: oral, intravaginal, transdermal; progestogen-only: oral, implanted, and injected) **in conjunction with** a barrier method (preferably male condom). Highly effective methods further include intrauterine device (IUD), intrauterine hormone-releasing system (IUS), bilateral tubal occlusion, vasectomised partner (provided that the partner is the sole sexual partner of the subject and the vasectomised partner has received medical assessment of the surgical success) and sexual abstinence, i.e. when this is in line with the preferred and usual lifestyle of the subject.

Women of child-bearing potential will undergo sensitive urinary pregnancy tests (hCG, human chorionic gonadotropin).

Pregnancy discovered during the clinical trial must lead immediately to exclusion (if at screening) or withdrawal of the subject.

If the subject has already received IMP, the pregnancy will be documented on a pregnancy report form. The case must be reported within 24 hours of knowledge to the CRO's pharmacovigilance delegate or the CRA. The subjects will be asked to report also pregnancies within 3 months after (regular or premature) termination of the trial to the investigator.

The investigator must follow up on pregnancies discovered after IMP administration until the end of pregnancy to document the outcome on the pregnancy outcome report form.

